# Table 1. Dosage and duration of treatment with rivaroxaban according to licensed and

## proposed indications. [1;5;10-12]

Indication	Initial dose (mg)	Maintenance / maximum dose	Duration	Food intake
Prevention of VTE in adult patients undergoing elective major hip or knee replacement surgery	10 Initial dose should be taken 6 to 10 hours after surgery provided that haemostasis has been established	10	For patients undergoing major hip surgery, -5 weeks For patients undergoing major knee surgery - 2 weeks	Can be taken with or without food
Treatment of DVT and prevention of recurrent DVT and PE in adults	15 (twice daily for first 3 weeks)	20 (daily)	Continued treatment	To be taken with food
Treatment of PE and prevention of recurrent DVT and PE in adults	15 (twice daily for first 3 weeks)	20 (daily)	Continued treatment	To be taken with food
Treatment of DVT and prevention of recurrent DVT and PE in adults (in patients with moderate or severe renal impairment) §	15 (twice daily for first 3 weeks)	15 (daily)	Continued treatment	To be taken with food
Prevention of stroke and systemic embolism in adult patients with non-valvular atrial fibrillation with one or more risk factors, such as congestive heart failure, hypertension, age $\geq$ 75 years, diabetes mellitus, prior stroke or transient ischaemic attack	20 (daily)	20 (daily)	Continued treatment	To be taken with food
Prevention of stroke and systemic embolism in adult patients with non-valvular atrial fibrillation with one or more risk factors, such as congestive heart failure, hypertension, age $\geq$ 75 years, diabetes mellitus, prior stroke or transient ischaemic attack (in patients with moderate or severe renal impairment)	15 (daily)	15 (daily)	Continued treatment	To be taken with food

<sup>§ In patients with moderate (creatinine clearance 30 - 49 ml/min) or severe (creatinine clearance 15 - 29 ml/min) renal impairment the following dosage recommendations apply:

For the treatment of DVT and prevention of recurrent DVT and PE: Patients should be treated with 15 mg twice daily for the first 3 weeks. Thereafter, the recommended dose is 15 mg once daily based on PK modelling

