From rivaroxaban clinical trial data, the cumulative incidence of each of the primary outcome major bleeding events (GI, urogenital and intracranial) in patients taking rivaroxaban for DVT and prevention of recurrent DVT and PE over 12 weeks of treatment was approximately 0.2%, 0.1% and 0.0%, respectively. Since information on the reported incidence for intracranial major bleeding outcomes within the first 12 weeks of treatment is limited, the reported incidence of intracranial haemorrhage with enoxaparin/vitamin K antagonist (VKA) from RCTs of 0.1% within 12 weeks will be used as an estimate of the incidence of that event in this population for rivaroxaban. From clinical trial data, the cumulative incidence of the primary outcome major bleeding events was similar in patients taking rivaroxaban for PE (~0.3%). As such, we do not expect any difference in cumulative incidence of bleeding between PE and DVT patients.

The formula used to calculate the sample size based on an estimation of the proportion of patients who will experience major bleeding outcomes is[33]:

Sample size= 
$$3.84 \times p(1-p)$$
 \_where p= estimated proportion (cumulative incidence)  
(precision)

Thus in this population of patients taking rivaroxaban for the treatment of DVT and PE and prevention of recurrent DVT and PE, in order to estimate the expected (true) cumulative incidence of the primary outcomes of major bleeding (GI, urogenital and intracranial) of 0.4% (0.2%, 0.1% and 0.1%, respectively), within  $\pm 0.39\%$ , we would need a sample size of 1005 patients (Epi Info v6).

The cumulative incidence of each of the primary outcome major bleeding events (GI, urogenital and intracranial) in patients taking rivaroxaban for the prevention of stroke and systemic embolism in adult patients with non-valvular atrial fibrillation over 12 weeks of treatment was approximately 0.5%, 0.1% and 0.1%,‡‡‡ respectively. [5] Thus, in this population of patients taking rivaroxaban for the prevention of stroke and systemic embolism in adult patients with non-valvular atrial fibrillation, in order to estimate the expected (true) cumulative incidence of the primary outcomes of major bleeding (GI, urogenital and

<sup>‡‡‡ Approximate estimates of cumulative incidence in 12 weeks of treatment, based on steady increase in incidence over time and overall cumulative incidence from a median of 590 days treatment exposure (90/590\*N)

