# Total number of new cases during 12 week observation period x 100 Population initially at risk

If the observed cumulative incidence from the SCEM study falls within the range expected as set by the precision limits of cumulative incidence from clinical trial data, then the null hypothesis (of no difference) will not be rejected. Cumulative hazard rate methods account for truncation of exposure time and censoring; for these analyses the exposure time would be censored at the time of the first event. Kaplan-Meier plots will be presented to describe timeto event as well as smoothed hazard plots to describe how the baseline risk of an event changes over time. Estimates of the hazard function will also be modelled to determine whether the baseline hazard (risk) of the event increases or decreases with time. A constant hazard over time may be consistent with a background (not caused by the drug) event rate, whereas a non-constant hazard over time may be an indicator of a drug-event relationship. The null hypothesis that the hazard rate of the selected event in patients prescribed rivaroxaban will be constant during the 12 week period following the start of treatment will be tested by fitting a parametric time to event model (e.g. Weibull). Such models have a shape parameter that indicates whether the hazard is significantly increasing or decreasing over time. At least five reports of an event are deemed necessary for modelling purposes.\*\*\*\*\*\*

Several sensitivity analyses will be performed: In one, observation start date will be imputed to be the same as the diagnosis date (i.e the index date will be shifted backwards in time) for those patients for whom a lag period between diagnosis and receiving rivaroxaban treatment was reported. The application of time-varying covariates methodology will enable examination of the impact of any transition from other treatments given as part of initial standard care on the results. In addition, since the primary analysis will be run only to include confirmed cases of incident major bleeding, it will be necessary to explore the reasons for exclusion of incomplete cases and examine their impact on the estimated measure of frequency.

Where possible, data will be stratified according to relevant strong risk factors (e.g. gender, age ( $\leq 60, 60-74, \geq 75$  years), indication and past history of haemorrhage or VTE) and stratum-specific incidence rates examined.

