Graphs of cumulative counts of events of interest, by month over the study period, will be examined for possible change in reporting over calendar time.

4.7.3. To describe the health profile of patients at index date prescribed treatment with rivaroxaban in the secondary care hospital setting and the treatment programme they received to advance the understanding of the rivaroxaban patient population in actual clinical practice in relation to the contextual cohort.

\*\*\*\*\*\* e.g. when the shape parameter (p) for the Weibull model is equal to one, the hazard is estimated to be constant over time, if p is greater than one the hazard is increasing, if p is less than one the hazard is decreasing. The hazard function will be determined as non-constant if the 95% CI excludes the value one

The following relates to Section 2.2.2 secondary objective (ii). Valid cohort demography (patient self-reported: age, gender, ethnicity, socioeconomic index) will be presented separately for both rivaroxaban and the contextual cohort, as reported at index date using all available information from questionnaires (completed by patient and specialist HCP). Other patient self-reported general health factors [BMI, weight, height, smoking and alcohol use] and indication-related characteristics [primary (and secondary if provided) diagnosis/decision, date and duration since first ever recorded; stroke and reported bleeding risk factors; pattern of most recent INR/APTT levels if switching from prior anticoagulant]; anticoagulant treatment initiation programme by specialist HCP (index date, dose and frequency) and non-clinical prescribing reasons. A synopsis of pre-index and concurrent relevant morbidities and medication use will also be provided.

For rivaroxaban cohort only, patient subgroups of special interest (Table 5 – 'off-label' use defined as arising from contraindications and those for which: a) precautions for use are recommended; b) appropriate clinical monitoring is recommended; c) limited information is available; and d) selected concomitant drug use) will be summarised in order to inform on real-life use of rivaroxaban. The proportion of patients within each special population sub-group prescribed rivaroxaban who had *one or more* relevant characteristics/conditions/co-prescribed medications at index date will also be summarised within each indicator group by simple aggregation of counts (Table 5).

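### Section 4.7.2 should not read a constant or non-significant Weibull shape for bleeding as pointing to a background rate

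*Supplement*

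**What the plan says.** Section 4.7.2 covers the primary objective, bleeding in rivaroxaban users. Beside the cumulative incidence it plans a model of the hazard over time. The null hypothesis that the rivaroxaban hazard "will be constant during the 12 week period following the start of treatment will be tested by fitting a parametric time to event model", with Weibull as the example. The interpretation has two limbs. The first is that "A constant hazard over time may be consistent with a background (not caused by the drug) event rate". The second is that a hazard which changes with time could point to a link between the drug and the event. The footnote gives the rule: "The hazard function will be determined as non-constant if the 95% CI excludes the value one". On data requirements: "At least five reports of an event are deemed necessary for modelling purposes".

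Three other places bear on this.
- Sections 1.3.2 and 2.2.1 list haemorrhage as an important identified risk.
- The footnote in section 4.2.1 says the 12-week AF reference risks are approximate and "based on steady increase in incidence over time and overall cumulative incidence from a median of 590 days treatment exposure", scaled by 90/590. No such note is attached to the DVT/PE figures.
- Table 1 shows a change of regimen after the first three weeks for DVT/PE and none within 12 weeks for AF.

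Stratification by indication is planned where possible, for incidence rates. No shape model by indication and no change point at three weeks is stated.

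**The concern.** The question for this outcome is not whether rivaroxaban can cause bleeding; the plan already treats that as known. If bleeding on a fixed daily regimen accrues steadily, as the AF reference figures assume, a drug effect appears as a higher level of a flat hazard. That is the pattern 4.7.2 says may be background. A single-cohort shape test looks only at how events are spread over the 12 weeks and not at how many there are.

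The other limb has a separate difficulty. In DVT/PE the regimen changes after day 21, while the acute illness and the transition from earlier treatment also evolve over the same weeks. A Weibull hazard can only rise or fall smoothly, and it is described for all rivaroxaban patients together. It cannot isolate a step at day 21 in one indication.

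At stake is the wording of the report on the primary outcome: a null shape test, likely at these counts, could be presented as compatible with bleeding not caused by the drug.

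**Working it through.** **Inputs.** From 4.2.1: 12-week risks (GI, urogenital, intracranial) of 0.2%, 0.1%, 0.1% in DVT/PE (total 0.4%) and 0.5%, 0.1%, 0.1% in AF (total 0.7%); minimum sizes 1005 and 561; total 1700. From 4.7.2: at least five events; 95% CI rule. Assumed: 1700 split as 1139 DVT/PE and 561 AF (the plan's 1:2 ratio gives nearly the same), full 12-week follow-up, and the early hazard ratios below.

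**The plan's own figures.** n = 3.84 p(1−p)/precision².
- DVT/PE: 3.84 × 0.004 × 0.996 / 0.0039² = 1005.8 (stated 1005).
- AF: 3.84 × 0.007 × 0.993 / 0.0069² = 560.6 (stated 561).

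Both reproduce. No power is stated for the shape test. As a check on the AF scaling, the appended product label gives 0.49 intracranial bleeds per 100 patient-years; 0.49 × 84/365.25 = 0.11%, against the stated 0.1%.

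**Expected events in 1700.**
- GI: 1139 × 0.002 + 561 × 0.005 = 5.1; chance of at least five, 57%.
- Urogenital and intracranial: 1700 × 0.001 = 1.7 each; chance of at least five, 3% each.
- All three sites: 1139 × 0.004 + 561 × 0.007 = 8.5; chance of at least five, 92%.
- By indication at the minimum sizes: 4.0 in DVT/PE (38%) and 3.9 in AF (36%).

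**Why the level drops out.** For rare events over 84 days the shape estimate is d / Σ(−ln(t/84)), where d is the number of events and t their times, and SE(log shape) = 1/√d. The risk level enters only through d. The 95% CI is the estimate multiplied and divided by exp(1.96/√d): a factor of 2.40 at 5 events and 2.00 at 8. An estimate of exactly one has an interval of 0.42-2.40 or 0.50-2.00.

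**Simulation** (40,000 studies per row, pooled cohort, fitted when d ≥ 5; the early ratio applies to DVT/PE on days 1-21 and AF stays constant):

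| Truth | CI excludes one | Declared decreasing | Declared increasing |
|---|---|---|---|
| Constant, reference risk | 6.2% | 1.0% | 5.1% |
| Constant, three times the risk | 5.3% | 1.5% | 3.8% |
| Early ratio 1.5 | 5.2% | 1.8% | 3.4% |
| Early ratio 2 | 5.1% | 2.9% | 2.3% |
| Early ratio 3 | 6.2% | 4.9% | 1.3% |
| Early ratio 5 | 9.3% | 8.7% | 0.6% |

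Tripling a constant risk leaves rejection near its nominal level. At an early ratio of 1.5 the test points the wrong way more often than the right way. For a true Weibull shape of 0.7, power is 10% at 5 events and 14% at 8; for 0.5 it is 29% and 45%.

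**Two-period comparison.** Given d events, the number on days 1-21 is binomial with probability 21r/(21r + 63): 0.25 if the hazard ratio r is 1, and 0.5 if r is 3.
- d = 5: four or more early events has probability 0.0156 under r = 1, so four suffice; at r = 3 the chance is 6/32 = 19%.
- d = 8: six are needed (0.0042; five gives 0.0273); at r = 3 the chance is 37/256 = 14%.
- d = 4: all four must be early; at r = 3 the chance is 1/16 = 6%. A 2/2 split gives a ratio of 3 with an exact 95% CI of about 0.22 to 41.

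With the threefold excess given to all events in the same way, the Weibull rule declares a decreasing hazard in about 5% (5 events) and 10-11% (8 events).

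**The case against.** The text is hedged: both limbs say may, and neither is a rule for deciding causation. Sections 4.4.2.5 and 4.8 reserve conclusions on drug-relatedness for an aggregate assessment by independent assessors, in which time to onset is one consideration among several. Section 4.7.5 describes such models as a tool for signal generation. Kaplan-Meier plots, smoothed hazard plots and weekly incidence densities are planned, so an early cluster could be seen. Section 4.7.2 also plans time-varying covariates for earlier treatment and a sensitivity analysis that moves the start date. The two-period comparison is itself weak at four events.

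Most of this stands, and it limits the point. A reader might infer that the test cannot inform on causation at all, that the plan would formally reclassify bleeding as background, or that an early excess would go unseen. The documents do not support these readings, for the reasons just given. Nor do they support extending steady accrual to DVT/PE, since the footnote covers AF only. A fall in hazard after day 21 could itself be drug-related, in line with the plan's second limb; the difficulty is separating it from the course of the disease.

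What the objection does not answer is the sentence itself. The signal-generation description sits under other events, whereas 4.7.2 applies the background reading to a known risk, with no caveat about power or non-rejection. The planned plots do not correct that reading.

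**Conclusion.** The concern holds in limited form. For haemorrhage, a constant or non-significant shape is not evidence against drug causation, because the shape ignores an even rise in hazard (6.2% against 5.3% rejection when the risk is tripled). At about 5 GI events, or 8 to 9 in all, it also has little power: 5% to 9% for early DVT/PE hazard ratios of 1.5 to 5. A monotone model for the whole cohort cannot isolate the regimen change in DVT/PE.

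These figures rest on the plan's reference risks, the assumed split and hazard ratios, and full follow-up without early stopping. Non-rejection is not inevitable: a shape of 0.5 would be found in 45% of studies with eight events. Nor do the documents show that the Weibull model must be withdrawn; it can describe the data. The matter affects interpretation of an auxiliary analysis of the primary outcome, not the incidence estimate.

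**What to change.** In section 4.7.2:

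1. Remove the background reading of a constant hazard for haemorrhage, or confine it to signal generation for unlabelled events.
2. State that failure to reject a constant hazard is not evidence against a drug effect.
3. For DVT/PE, report event counts and rates for days 1-21 and days 22-84, with their ratio and exact 95% CI, as description and not as a test. Show AF separately. Keep the Weibull model as a supplementary description.

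The cost is a few sentences and one small table; start dates, posology and event reports are already to be collected. The drawback is very wide intervals, with about four events expected per indication at the minimum sizes, often below the plan's own five-event threshold for modelling. The table should say so.

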#### 4.0 METHODS

#### 4.1 Study Design & Time frame

This study will be a registry-based observational, population-based cohort study with an internal contextual cohort utilising the technique of cohort event monitoring to study the short-term (up to 12 weeks) safety profile and use of rivaroxaban prescribed by specialist HCPs in the secondary care hospital setting in the immediate post-marketing period for the licence extension. Twelve weeks observation is regarded as a period of time sufficient for data from all relevant patient populations (which informs on any post start of observation health events related to short-term exposure that they might have experienced) to be recorded in the patient's medical charts by specialist HCP. Randomisation will not be required. Once the pharmacotherapeutic treatment decision has been made, and either rivaroxaban or the alternative anticoagulation therapy prescribed as the most appropriate treatment based on clinical need, a patient will be invited to participate in the study and consent obtained for access to information from medical charts (see section 3.0).

Study start is defined as the date that the first patient is recruited into the study, which is anticipated to begin May 2013 (*exact date to be confirmed*) and continue for a maximum of 36 months, or until the target sample size for both cohorts has been achieved (whichever is the soonest); see section 4.2. The final cohort sizes, period of observation and the duration of the SCEM study will be dependent on the level of prescribing of rivaroxaban by specialist HCPs in England and Wales (see section 4.2). Data collected during later time periods can be compared with earlier periods to identify any trends that may be emerging. Slow uptake may impact on the ability to meet the study objectives; in this instance the need to continue data collection, extend the observation period and the feasibility of study completion within the proposed time frame should be open to re-evaluation.

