intracranial) of 0.7% (0.5%, 0.1% and 0.1%, respectively), within  $\pm -$  0.69%, we would need a sample size of 561 patients.

Thus, in summary, for this study, a minimum sample size of 1700 evaluable patients for rivaroxaban is desirable to ensure the minimum of 1005 and 561 patients is achieved for each of the two indications described above for each drug, based on ratio of 1:2 respectively, with 12 weeks observation period sufficient to estimate cumulative incidence of specified primary outcomes of interest with desired precision. A similar number of evaluable new user alternative anticoagulant therapy patients will be collected for the internal contextual cohort.

In this study, sample size has been calculated such that the study estimate of cumulative incidence of major bleeding within each indication should fall with a pre-specified proportion which is relative to the true value. There is no ideal precision which should be used when calculating sample size, so use of proportion as an indicator of relative precision ensures the margin of error remains appropriate to the estimated size of cumulative incidence of major bleeding events.

Table 3. Sample sizes of evaluable patients required to estimate the expected (true)
cumulative incidence of a specified adverse event with 95% confidence intervals of
different precisions (0.2% to 5%).

Incidence	Precision							
from RCT	0.20%	0.39%	0.50%	0.69%	1%	2%	3%	5%
(%)								
0.10	958	252	153	81	38	10	4	2
0.20	1913	504	307	161	77	19	9	3
0.30	2864	755	459	241	115	29	13	5
0.40	3812	1005	612	321	153	38	17	6
0.50	4755	1255	764	401	191	48	21	8
0.70	6631	1752	1067	561	267	67	30	11
0.80	7564	2000	1218	640	305	76	34	12
1.00	9418	2494	1519	798	380	95	42	15
2.00	18475	4926	3003	1579	752	188	84	30
3.00	27187	7296	4452	2342	1117	279	124	45
4.00	35566	9605	5866	3089	1473	369	164	59
5.00	43627	11854	7246	3818	1821	456	203	73

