# 4.7.2 To estimate the cumulative incidence of the important identified risk of haemorrhage for rivaroxaban.

The following relates to Section 2.2.1 primary objective (i) for rivaroxaban only and relates to haemorrhage within gastrointestinal and urogenital organ sites (which meets the criteria for a major bleed) and all intracranial sites (as defined in Table 2)..

For the three organ sites specified in the primary outcome, each of the individual components of the major bleeding criteria (a fall in haemoglobin of 2 g/dL or more, or a transfusion of 2 or more units of packed red blood cells or whole blood, or a fatal outcome - as per table 2) will be summarised. Where an individual has one or more criterion for an individual organ site of interest, this will also be summarised – in such individuals the first report will be regarded as the incident event. The cumulative incidence (risk) of the primary outcomes reported during treatment within the 12 week observation period will be explored by estimating the cumulative incidence of incident reports (plus 95% CI) and cumulative hazard rates (plus 95%CI) of incident events over time. For purposes of this analysis the denominator (personperiod at risk) is defined as the 12 week observation period (i.e., the time from the date the first prescription was issued for rivaroxaban (treatment index date) until the date of stopping (+ 2 days) or at 12 weeks if patient did not stop, whichever occurs first). The numerator will comprise of reports of incident major bleeding events during that 12 week observation period. These which have been adjudicated by expert review (using all available information from SCEM questionnaires, follow-up and any additional documentation). Where such information reveals that the event was misreported, that patient will excluded as a case from the analysis, but contribute person-time exposed.

The cumulative incidence will be calculated according to the formula:

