The following relates to Section 2.2.2 secondary objective (iii) Status of indication-related characteristics (alteration of diagnosis, stroke (CHADS2/ CHA2DS2-VASc) and bleeding risk score (HAS BLED) if available) will be summarised, plus pattern of anticoagulant treatment adherence at the end of the 12 week observation period (as estimated from Medication Possession Ratio††††††) will be summarised. The frequency and reasons for attendance to clinics for review and management of anticoagulation and/or acute hospitalisations (including hospital referrals) will also be summarised, where reported. Alterations in treatment programme (change in dose, other drugs) will be described, as will any reason(s) for stopping treatment (including switching) and transition plans to other anticoagulants.

Changes in these indication-related characteristics and treatment details will be examined by comparing values at index and at 12 weeks post index date. Exploratory analysis may include data mining and descriptive measures for describing alterations in treatment programme.

The number of pregnancies, trimester of first exposure and details of births, terminations and miscarriages will be presented. The number of deaths (as recorded in medical charts) in the total cohort for each month of exposure will be calculated. Causes of death will also be described by system-organ class.

Sensitivity analyses will examine any under-reporting using data provided from the patients GP.

Where no. days held will be calculated from information derived from 12 week questionnaire on number of prescriptions and average treatment length of prescriptions (usually given in 7, 14,28,56 day repeats); no. days supply expected will assume chronic use from start to end of study observation or treatment stop date (if stopped)

4.7.5 To quantify the incidence risk and rate of events reported in the 12 week observation period in both the rivaroxaban and contextual cohort and in patient subgroups of special interest.

The following relates to Section 2.2.2 secondary objectives (i) and (iv) regarding a) major bleeding outcomes as specified in the primary objective for the contextual cohort, b) other major or non-major clinically relevant bleeding outcomes not specified in the primary objectives, c) thromboembolism (recurrent and incident) and d) any other events reported in the 12 week observation period.

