# 5.2 Limitations

- Possible delay in new user cohort accrual if adoption by secondary care hospital trusts and specialists is low.
- Since this is an observational epidemiological study, we recognise several potential sources of bias. The most important is selection bias and the possibility that the cohorts will not be representative of the general population for whom anticoagulation is clinically desirable. Because of the prospective nature of patient recruitment, bias in recruitment may be introduced by some participating specialist HCPs through awareness of some form of remuneration (regardless of how and when payment is made). This study does not look at the comparative early safety profile of rivaroxaban in the context of initiations of other novel anticoagulants; therefore the extent of selection bias cannot be established in regard to those treatments. However the same number of patients treated with warfarin for similar indications will be collected to explore factors which may contribute to selection bias. Furthermore, the characteristics of patients providing consent to those who do not will be compared in order to identify possible systematic differences between such patients.
- Knowledge of which patients will be participating may affect the non-interventional nature of observational research. Exclusion of patients initiated on treatment between date of market launch and study start may also add to selection bias. Nevertheless patient identification (case ascertainment) is likely to be more complete than through retrospective methodology; this may also minimise bias introduced by non-participation of patients. It is also possible that specialist HCPs who participate in the study will be a self-selected group, but we do not believe that this selection bias will affect the types or number of events experienced and reported by a patient after treatment has been initiated. An instrumental variable reflecting physician prescribing preference will be explored to control for unmeasured confounding possibly associated with treatment decisions.

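### The calendar-time check on event reporting uses cumulative counts with no denominator, so it cannot separate recruitment pace from a change in reporting

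*Supplement*

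**What the plan says.** The commitment stands at the end of Section 4.7.2: "Graphs of cumulative counts of events of interest, by month over the study period, will be examined for possible change in reporting over calendar time." Neither patients nor person-time under observation is mentioned.

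The surrounding design is this:

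- Section 4.1: recruitment will "continue for a maximum of 36 months, or until the target sample size for both cohorts has been achieved", whichever comes sooner.
- Section 4.7.2: a patient's time at risk runs from the treatment index date "until the date of stopping (+ 2 days) or at 12 weeks if patient did not stop, whichever occurs first".
- Section 5.2 lists as a limitation "Possible delay in new user cohort accrual if adoption by secondary care hospital trusts and specialists is low". Section 4.9.2 adds that accrual will depend on managed entry and on how trusts apply NICE guidance.
- Section 4.1 also remarks, without giving a method: "Data collected during later time periods can be compared with earlier periods to identify any trends that may be emerging."
- Section 4.7.3 allows stratification by calendar period as an option, under the description of health profile. It names no rate.

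For deaths, Section 4.7.4 says: "The number of deaths (as recorded in medical charts) in the total cohort for each month of exposure will be calculated." It gives no denominator and does not define a month.

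**The concern.** Patients enter over as long as three years, and each contributes at most 12 weeks. The expected number of events in a calendar month is therefore the product of three things: the event rate, the proportion of events that get reported, and the number of patients under observation that month. A cumulative count shows only the product. If recruitment speeds up, the curve steepens with no change in risk or reporting. If recruitment speeds up while reporting declines, the two can cancel.

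This is the only calendar-time check of event reporting that the plan commits to, in a safety study whose own limitations (Section 5.2) name under-reporting, and time bias if collection is extended. At stake is either a false impression of drift or false reassurance that there was none.

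**Working it through.** **The plan's own figures.** Section 4.2.1 uses n = 3.84 × p(1 − p) / precision².

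- DVT/PE: 3.84 × 0.004 × 0.996 / 0.0039² = 1005.8 (stated 1005).
- AF: 3.84 × 0.007 × 0.993 / 0.0069² = 560.6 (stated 561).

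Both reproduce. Expected primary events are 1005 × 0.004 + 561 × 0.007 = 4.02 + 3.93 = 7.9. Section 4.2.1 says "a minimum sample size of 1700 evaluable patients for rivaroxaban is desirable". At 1700 patients split about 2:1, the figure is 1134 × 0.004 + 566 × 0.007 = 8.5. So about 8 primary events are expected in the rivaroxaban cohort.

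**Effect of accrual on the counts.** The documents give no monthly accrual, so the patterns below are assumptions. Let a(m) be the number entering in month m, with each patient contributing three months at a constant rate. Patients under observation in month m are a(m) + a(m−1) + a(m−2), and expected events are proportional to that sum. The level of risk cancels from the ratios.

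| Assumed accrual | Months 1-12 | Months 25-36 | Ratio of counts | True rate ratio |
|---|---|---|---|---|
| Flat, a(m) = 1 | 1 + 2 + 10 × 3 = 33 | 12 × 3 = 36 | 36/33 = 1.09 | 1 |
| Doubles at month 19 | 33 | 12 × 6 = 72 | 72/33 = 2.18 | 1 |
| Linear ramp, a(m) = m | 1 + 3 + 3 × (2 + … + 11) = 199 | 3 × (24 + … + 35) = 1062 | 1062/199 = 5.34 | 1 |

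**A hidden fall.** If accrual doubles at month 19 and reporting halves by months 25-36, the count ratio is 2.18 × 0.5 = 1.09. That is exactly what flat accrual with unchanged reporting gives.

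**The same effect at the size of the primary outcome.** Take 1700 patients, 84 days each, about 8 events in all at constant risk. Compare the first 18 months with the remainder, which includes the follow-up of the last entrants:

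| Assumed accrual | First 18 months | Remainder | Ratio |
|---|---|---|---|
| Uniform | 3.70 | 4.32 | 1.17 |
| Linear ramp | 1.71 | 6.30 | 3.68 |
| Second half three times as fast | 1.85 | 6.17 | 3.33 |
| First half three times as fast | 5.55 | 2.47 | 0.44 |

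Dividing by person-time returns a rate ratio of 1.0 in every row.

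**Deaths by month of exposure.** Twelve weeks is 84 days. With months of length L, the third month holds 84 − 2L days:

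- L = 28: 28 days, no shortfall.
- L = 30: 24 days, 24/30 = 0.80.
- L = 30.44: 23.1 days, 23.1/30.44 = 0.76.

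Separately, suppose a proportion d stops treatment by week 12 at a constant hazard, and deaths are counted only while exposed. With 28-day months, the third-month count relative to the first is then (1 − d)^(56/84). This gives 0.93, 0.86 and 0.79 for assumed d of 10%, 20% and 30%. Per patient-week, all of these return to 1.0.

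**The case against.** The strongest reply is that the plan is not short of person-time. Section 4.7.5 sets out weekly incidence densities per 1000 patient-weeks for all events, and Section 4.7.2 plans Kaplan-Meier, smoothed hazard and Weibull analyses that deal with censoring. Accrual is reviewed monthly (Section 4.5.1) and given in progress reports (Section 4.9.2). The graphs carry no threshold, test or decision rule. With about 8 primary events, even a rate plot would show little, and flat accrual distorts the comparison by only 9%.

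Much of this stands. A reader might infer that the plan lacks person-time altogether, but that is true only of the two displays discussed here. A reader might also infer that the primary estimate is affected, but the graphs do not feed it. The general remark in Section 4.1 about comparing periods specifies no count-only analysis and is not evidence of the fault.

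The deaths table invites two further over-readings. The first is that it is another check of reporting. It is a description by time on drug and says nothing about calendar time. The second is that month 3 must show about 24% fewer deaths. That follows only if months are calendar months. The documents leave the month undefined, and 12 weeks is exactly three 28-day months.

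The reply does not repair the calendar graph. The planned rates and time-to-event analyses all run on time since treatment start. Calendar stratification is optional and names no rate. The accrual figures are not tied to the graphs.

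**Conclusion.** The point holds for the calendar-time graphs. As specified, they confound recruitment pace with any change in risk or reporting. At constant risk and reporting, the last-year to first-year count ratio ranges from 1.1 to 5.3 over the accrual patterns tried, against a true rate ratio of 1. Front-loaded accrual pushes the ratio below 1: 0.44 for the remainder against the first 18 months. These sizes rest on assumed accrual. What the documents support is that accrual is expected to be uneven, not how uneven. The consequence is confined to an exploratory check.

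The deaths display is a lesser matter. With no denominator and no defined month, later counts could be lower at constant risk because patients stop or because the third month is short. The short-month shortfall is 20-24% with 30-day or calendar months and nil with 28-day months. This concerns the pattern by time on drug, not reporting over calendar time.

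**What to change.** In Section 4.7.2, replace the cumulative-count graphs with one of two displays:

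- events per 1000 patient-weeks under observation by calendar period, with 95% confidence intervals; or
- observed cumulative counts against those expected from accrued person-time at the overall rate.

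For the primary outcome, use quarters or half-years by index date rather than months. Eight events over 36 months is about 0.2 per month, and over six half-years about 1.3 per period. The intervals will be wide, and the report should say so. Monthly display can be kept for commoner events.

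In Section 4.7.4, define the month as 4 weeks, state whether deaths after stopping are counted, and report deaths per 1000 patient-weeks in three 4-week periods alongside the counts.

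The cost is wording and a little programming. Index and stop dates are already collected (Sections 4.4.2.2 to 4.4.2.4), and patient-weeks are already computed for the incidence densities in Section 4.7.5. No new data, patients or site work are needed.
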